 10.00 Gy (RBE)
 4.00 Gy (RBE)

5. Brainstem 67.00 Gy(RBE) to the anterior surface, 55.00 Gy (RBE) to the

center and 50.00 Gy (RBE) to the posterior surface

6. Cochlea 60.00 Gy (RBE) (point dose, 30.00 Gy (RBE) to the contralateral,

if well lateralized lesion

7. Spinal cord 45.00 Gy (RBE) (if base of skull primary; same constraints as

brain stem if spinal cord primary)

8. Pituitary 45.00 Gy (RBE)

9. Temporal Lobes Less than 10% to get prescription dose 10. Cerebellum Less than 10% to get prescription dose

Note: All planning parameters can be altered by the radiation oncology team as appropriate in order to deliver the prescribed dose and maintain sparing of the organs at risk if clinically acceptable to the treating physician

4.5.2 IMRT backup plans or partial treatments may be carried out as requested by the physician. The prescription is as specified above and administered using the same scheme. The planning target volume expansion margin defined on case by case basis from the CTV volumes .The lateral margins will be defined by the multi-leaf collimator and will wary between 0.3 to 1.5 cm or as found to be appropriate in order to have adequate coverage to sparing ratio.

#### **4.6** Treatment Duration

Proton radiation therapy will in most instances be completed within 9 weeks of the start of treatment. This may be extended if subjects require a break from treatment. Criteria for break would include any **Grade 3 or 4** toxicity, depending on the clinical situation as determined by the treating physician. All subjects experiencing Grade 4 toxicity considered probably or definitely related to radiation will be considered infeasible in the feasibility phase of the study.

Version: 04/04/2014

Continuation of treatment and/or further treatment plans will be decided at the discretion of their treating physician.

### 4.7 External Beam Equipment and Beam Delivery

Protons: A high energy proton beam will be used. Treatments will be administered at the University of Pennsylvania Roberts Proton Facility and will be 72.00-79.20 Gy (RBE) for chordomas and 70.20-73.80 Gy (RBE) for chondrosarcomas. All charged particle treatment will be given with the patient in the appropriate immobilization device.

Photons: A Varian Linear Accelerator will be used. Treatments will be administered at the University of Pennsylvania and will be included in the total dose prescribed above.

Film or digital images will be taken prior to the initial treatment to verify the position of the patient and the aperture and as appropriate. A radiation oncologist will check the first film on all fields. A radiation therapist will check subsequent films taken before treatment. All set-up films will be permanently filed for all subjects. Subjects will be treated employing a respiratory motion management technique to account for respiration as appropriate.

### 4.8 Quality Assurance

Daily portal films, and/or daily online radiographic imaging will be performed during therapy. Fiducials will help reproduce daily set up and minimize set up variations as appropriate. Implanted hardware may be used for localization purposes as well.

# 5.0 Chemotherapy

None

# **6.0 Study Procedures**

Patients will complete the Brief Fatigue Inventory and Fact Br which is specific to patients with CNS tumors. Fatigue and neurocognitive testing for these patients will continue for 3 years post radiation.

	Eligibility/ Pre- treatment	Weekly during treatment	1.1	O Follow-Up  X Months (approximat ely from completion of treatment) 3,6,9,12,15, 18, 21, 24 (approx.)	Months 30, 36 (approximatel y from completion of treatment)	1
Tests and						
Observations						
History and PE	X			X	X	X
ECOG Score	X		X	X	X	
CT/MRI	X			X	X	X

CXR	$X^3$					
Pathology	X					
Pregnancy Test	$X^1$					
Toxicity	X	X	X	X	X	X
Assessment						
Tumor	$X^2$			$X^2$	$X^2$	$X^2$
Measurement						
BFI (fatigue)	X	X	X	X	X	X
Fact Br (neurocog)	X	X	X	X	X	X

 $X^{I} A \text{ pregnancy test will be required for females of child bearing potential within 5 days of tx)}$ 

### 6.1 Post-treatment Evaluation and Follow-up

All subjects will be evaluated weekly during the course of the proton therapy, at the inspection visit (approximately 90 days from treatment start) and approximately every three months from the last dose of treatment either by the treating radiation oncologist or a referring physician for two years, and approximately every 6 months for year 3 and then yearly for years 4 and 5. Patients will be treated and followed for 90 days from the start of radiation treatment to determine feasibility and safety (acute toxicity) for the initial phase of the study before moving to the second phase of the study.

Each follow-up examination will consist of interval history and physical examination, including a neurologic evaluation and toxicity assessment. A Brief Fatigue Inventory and FACT-Br will also be obtained. Assessment of the disease by MRI will be performed at intervals of 3 months for 2 years and then every 6 months for year 3 and annually for years 4 and 5.

# 6.1.1 Tumor Response (RECIST criteria, if measurable disease)

**Target Lesions:** For patients with gross or residual disease present after surgery (if surgery is feasible).

Complete Response (CR): Disappearance of all target lesions.

**Partial Response (PR):** At least a 30% decrease in the sum of the longest diameters of target lesion, taking as reference the baseline sum of the longest diameters.

**Progressive Disease (PD):** At least a 20% increase in the LD of the target lesions, taking as reference the smallest sum of the LD recorded since the treatment started or the appearance any new lesion(s).

**Stable Disease (SD):** Neither sufficient shrinkage to qualify for PR nor sufficient increase to qualify for PD, taking as reference the smallest sum LD since the treatment started.

### **6.1.2** Confirmation of Response

To assign a PR or CR, changes in tumor measurement must be confirmed by repeat assessments no less than 4 weeks after the criteria for response are first met.

 $X^2 Applicable if there is residual tumor)$ 

X As clinically indicated.)

To assign SD, measurements must have met the stable disease criteria at least once after study entry at 3 month intervals.

Local failure is defined as: evidence of tumor growth in any direction beyond that present of the pre-treatment imaging studies or the appearance of tumor in tissues previously scored as sites of subclinical disease. The imaging studies are to be comparable in technical factors.

Marginal failure is defined as: appearance of tumor growth at the margin of the target volume.

Overall Survival: Duration measured from date of first treatment until death or censored at date of last follow-up for patients still alive.

#### 7.0 Statistical Plan

#### 7.0 Statistical Considerations

This is a study of proton therapy for patients with chordomas and chondrosarcomas. The trial will be conducted in two phases. First, a feasibility study and then, a phase II study. Since proton is a new treatment modality at PENN, the first proton trial conducted in each cancer site will be a feasibility study, in order to gain experience on both the logistics of proton planning, dosimetry, scheduling and delivery, and patient safety issues.

#### 7.1 FEASIBILITY STUDY

# 7.1.1 Design and Objectives

The primary objectives are to determine feasibility and safety (acute toxicity). Secondary objectives are to determine late toxicity, long-term clinical outcomes and, fatigue and neurocognitive function.

Twelve patients will be enrolled and followed for a minimum of 90 days after start of radiotherapy to determine feasibility and acute toxicity. We expect to screen/enroll approximately 18 subjects to reach the goal of 12 evaluable subjects. A subject will be considered evaluable if they willingly remain on the study up until their first follow up visit. [note: a subject is still evaluable even if they are unable to undergo proton treatment as defined in section 2.0 or have a significant acute toxicity as these are feasibility criteria]. Ninety days of observation after start of radiotherapy will be required in all 12 patients prior to commencing the second phase of the trial. Patients enrolled in the feasibility study will continue to be followed beyond 90 days for the secondary endpoints of late toxicity, progression-free and overall survival fatigue and neurocognitive function.

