### **3.4** Early Withdrawal of Subjects

### 3.4.1 When and How to Withdraw Subjects

- Recurrent or Progressive Disease: Subjects who have clinical or radiologic evidence of recurrent disease will undergo an evaluation to document the nature of the abnormality. If recurrent or progressive cancer is diagnosed, the subject will be considered off study at that time.
- PI Decision: Subjects may be withdrawn at any time during the study if the PI believes it is in the subject's best interest. In this event, the reasons for withdrawal will be documented.
- Subject Participation: Refusal to continue treatment, follow-up, comply with the protocol or withdrawal of consent. In this event, the reasons for withdrawal will be documented.
- Adverse Event (including intercurrent illness, unacceptable toxicity).

Once the subject has discontinued treatment, the primary reason for discontinuing treatment must be clearly documented in the subject's records and on the CRF. The investigator will assess each subject for response at the time of withdrawal.

Every effort will be made to follow all subjects off study for toxicity and survival unless patient withdraws consent. If subjects withdraw from the study at any time, we will ask for his/her written permission to continue to access medical records for overall survival. Acute toxicities will be assessed for 90 days from the first date of treatment. Survival will be followed for a minimum of 5 years.

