### 7.1.2 Endpoints

### 7.1.2.1 Primary Endpoints

Feasibility will be based on multiple radiation planning and treatment parameters. For proton to be deemed feasible, no greater than 10% of patients should experience one of the following events: a) Patient cannot be given treatment because anatomy is such that a dosimetrically satisfactory treatment plan cannot be devised. For example, the dosimetry is unsatisfactory if

<95% of target volume is covered by 95% of the dose, b) Patient receives greater than 50% of their total treatment (for any reason-unable to set patient up within acceptable limits of tolerance, patient unable to tolerate treatment position or immobilization for duration of treatment) with photon beam radiotherapy (using a backup photon plan, c) Patient is unable to complete all of his/her treatments within 10 days of estimated date of treatment completion or requires a treatment break greater than 5 days.

Acute Toxicity is defined as any grade 3 or higher toxicity, considered probably or definitely related to radiation, observed within 90 days from start of therapy, excluding cranial nerve palsies or nerve root symptoms as these may be due to the tumor itself or prior surgery. Toxicities will be graded using the NCI Common Terminology Criteria for Adverse Events (CTCAE) Version 4.0.

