#### **Feasibility**

A feasibility rate  $\geq 90\%$  is considered acceptable. We will assume a beta (5,1) prior, which is information equivalent to feasibility established in 5 of 6 treated patients. If the number of patients in whom proton is deemed feasible is less than or equal to the number in the table below then termination will be considered as it is highly unlikely that the feasibility rate is  $\geq 90\%$ , as noted by the Bayesian posterior probabilities.

D ' D 1	C D '1 '1'	• ,				
Bayesian Rule	for Feasibili	ıty				
Patients treated in each stratum	3	6	9	1		
				2		
Patients in whom proton is	1	4	6	9		
feasible						
Posterior Prob[feasibility rate	0	0	0	0		
>90%]		•	•	•		
	0	0	0	0		
	4	9	4	8		
Action	Т	Terminate enrollment				

Acute toxicity will be divided into 2 categories to best characterize toxicities in this disease. Non-Neurologic Acute Toxicity

Because proton therapy is expected to spare normal tissues, a non-neurologic acute toxicity rate  $\leq 20\%$  is considered acceptable. We will assume a beta (1,5) prior, which is information equivalent to toxicity in of treated patients. If the number of patients with non-neurologic acute toxicity equals or exceeds the number in the table, then termination will be considered as it is likely that the toxicity rate is >10%, as noted by the Bayesian posterior probabilities.

Bayesian Rule for Non-Neurologic Acute Toxicity						
Patients treated	3	6	9	1		
				2		
Patients who experience acute	2	2	3	4		
toxicity						
Posterior Prob[toxicity rate	0	0	0	0		
>20%]			•			
	8	6	7	7		
	0	2	0	6		
Action	Te	Terminate enrollment				

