### 7.1.4 Statistical Analyses

Feasibility. The initial target sample size of 12 patients will be revised to 12 additional base of skull patients to be treated with pencil beam protons and evaluated for feasibility by the new definition. It is anticipated that up to 5 additional spine patients may be enrolled. So the total enrollment after this amendment will be up to 17 patients (12 base of skull and 5 spine). The statistical analysis will calculate the posterior probability that the feasibility rate is >90%. This analysis will be conducted 2 ways: based on all 26 patients treated and on all 17 patients treated after the modification. The definition of infeasibility will be that which was current when the patient enrolled on the trial. There will be no retroactive re-grading of infeasibility in the base of skull patients.

Acute Toxicity. All toxicities observed within 90 days from start of therapy will be graded by CTC Version 4.0 and tabulated. Special attention is paid to neurologic toxicity.

Late Toxicity. All toxicities observed later than 90 days from start of therapy will be graded by the CTCAE version 4.0 and tabulated.

Progression-free and overall survival will be estimated by the survival analysis methods. It is most likely that these time-to-event outcomes will be summarized as part of the phase II study.

Fatigue is scored on a 10-point scale based on the Brief Fatigue Inventory Questionnaire. At each time point, the BFI score will be summarized by mean and standard deviation, and plotted over time. We will examine the plots for the expected worsening of function in the 6-12 months post-radiation and gradual improvement from 12-24 months. The fatigue scores will be summarized in detail in the phase II study.

Neurocognitive function (FACT-Br) will be summarized by descriptive statistics and scatter plots. It is most likely that the neurologic outcomes will be summarized as part of the phase II study.

Estimation of Event Rates. The table below displays the 90% exact binomial confidence

intervals based on 12 patients treated.

intervals ous	ed on 12 patients	i catea.			
No. of	%	90%	No. of	%	90%
Events		exact	Events		exact
		CI			CI
0	0.0	17.5*	7	58.3	31.5,
					81.9
1	8.3	.43,	8	66.7	39.1,
		33.9			87.7
2	16.7	3.0,	9	75.0	47.2,
		43.8			92.8
3	25.0	7.2,	10	83.3	56.1,
		52.7			97.0
4	33.3	12.3,	11	91.7	66.1,
		60.9			99.6
5	41.7	18.1,	12	100.0	82.5*
		68.5			

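### Patients who withdraw before the first follow-up visit can be replaced and left out of the feasibility denominator, even when they stop for reasons of tolerance or side effects

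*Combined protocol and SAP*

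**What the plan says.** Section 7.1.1 defines who counts: "A subject will be considered evaluable if they willingly remain on the study up until their first follow up visit". It adds a protective note: "a subject is still evaluable even if they are unable to undergo proton treatment as defined in section 2.0". The note covers significant acute toxicity in the same way, because both are feasibility criteria. On numbers, the section states: "We expect to screen/enroll approximately 18 subjects to reach the goal of 12 evaluable subjects".

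Section 7.1.2.1 sets the limit: "no greater than 10% of patients should experience one of the following events". Event (a) is: "Patient cannot be given treatment because anatomy is such that a dosimetrically satisfactory treatment plan cannot be devised". Event (b) is a photon share of treatment above a stated percentage, and event (c) is failure to finish on time or too long a break.

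Section 3.4.1 lists the reasons for leaving the study. They include "Refusal to continue treatment, follow-up, comply with the protocol or withdrawal of consent" and, as a separate item, adverse events including unacceptable toxicity. Reasons must be documented.

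The statistical sections label the denominator differently. The feasibility table in 7.1.3 is headed "Patients treated in each stratum". Section 7.1.4 plans one analysis "based on all 26 patients treated" and a second on the 17 patients treated after the modification. No section says how a patient who withdraws before the first follow-up visit is scored, and no analysis of all enrolled patients is planned.

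**The concern.** Feasibility here means that patients can be planned, positioned, immobilised and taken through the course on time. Some of the reasons for which patients leave are failures of exactly that kind. A rule that keeps only those who choose to stay can remove such patients from the denominator and replace them, and whether a given patient was unable or merely unwilling would be judged after the outcome is known.

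The note in 7.1.1 closes only part of the gap. It does not clearly cover a patient who declines to go on before meeting a criterion, or one who leaves over side effects short of significant acute toxicity.

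Feasibility is the primary endpoint of the first phase, and 7.2 makes the start of phase II depend on it. With 12 or 17 patients and a 10% limit, the scoring of a single patient can change the result.

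**Working it through.** **Inputs.** Prior beta(5,1) and threshold 90% (7.1.3). Denominators 12 (7.1.1), 17 and 26 (7.1.4). About 18 screened or enrolled for 12 evaluable (7.1.1).

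**Formula.** With k feasible of n, the posterior is Beta(5+k, 1+n−k), and the quantity needed is P(rate > 0.90).

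**Reproducing the plan's figures.** At the boundaries 1/3, 4/6, 6/9 and 9/12 this gives 0.038, 0.090, 0.044 and 0.083. The table in 7.1.3 prints 0.04, 0.09, 0.04 and 0.08, so the method is the plan's own.

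**How many patients could be affected.** 18 − 12 = 6, and 6/18 = 33%. This is an upper limit, because the plan speaks of screening and enrolling together and does not give the split.

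**Effect of counting one left-out withdrawal as a failure** (assumption: the patient was in fact not feasible).

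| Evaluable only | Posterior | One failure added | Posterior |
|---|---|---|---|
| 12/12 = 100% | 0.833 | 12/13 = 92.3% | 0.550 |
| 11/12 = 91.7% | 0.518 | 11/13 = 84.6% | 0.266 |
| 17/17 = 100% | 0.902 | 17/18 = 94.4% | 0.685 |
| 16/17 = 94.1% | 0.661 | 16/18 = 88.9% | 0.408 |
| 26/26 = 100% | 0.962 | 26/27 = 96.3% | 0.844 |

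Two of these can be checked by hand. For 12/12, 1 − 0.9^17 = 0.833. For 12/13, 1 − (18 × 0.9^17 − 17 × 0.9^18) = 1 − 0.450 = 0.550.

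In the second and fourth rows, one patient moves the observed rate from above 90% to below it.

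**Effect on the termination rule.** From 12/12, adding one, two or three failures gives 0.550, 0.295 and 0.133. A fourth (12/16) gives 0.052, which lies in the 0.04–0.09 range of the plan's boundaries. From 11/12, three are needed (11/15, 0.043).

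**Direction.** If all six who left had been feasible, 18/18 would give 1 − 0.9^23 = 0.911, above 0.833. Exclusion raises the rate only if those excluded do worse than those kept.

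**The case against.** The strongest reply is that most relevant failures are already caught. Criterion (b) names set-up failure and intolerance of position or immobilisation, and criterion (c) catches a patient who cannot finish. The note retains untreatable patients and those with significant acute toxicity. What is left is mainly the unwilling patient, and nothing shows that this group consists of hidden failures.

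Much of this stands, and it narrows the point. It does not remove it. Criterion (b) is measured by the share of treatment given with photons, so a patient who simply stops need not meet it. Criterion (c) speaks of inability, and the plan does not say whether refusal counts as that. A patient who leaves during planning has no course to complete.

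A reader might go further and infer that untreatable patients drop out of the denominator, since a criterion (a) patient is never treated and the tables count patients treated. The documents do not support that. The note in 7.1.1 keeps these patients evaluable, the limit in 7.1.2.1 refers to patients without further restriction, and 7.1.4 and 7.3 give the same 17 as enrolment that 7.1.4 also calls treated. What remains is a conflict of wording.

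A reader might also set 33% non-evaluable against the 10% allowance, or quote 12/18 (posterior 0.006). Under 3.3, consent precedes screening and confirmation of eligibility, so the six may include screen failures, who do not belong in the denominator. That case is not realistic. It is also true that one to three added failures from 12/12 would not reach the termination range.

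**Conclusion.** The point holds for withdrawals. As written, 7.1.1 allows a patient who stops for reasons of tolerance or side effects to be left out of the primary denominator and replaced. This is a stated rule that depends on events after enrolment, not just a missing detail.

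One such patient, if truly not feasible, lowers the posterior by 0.28 at 12/12 (0.833 to 0.550) and by 0.22 at 17/17 (0.902 to 0.685). It can also take the observed rate across the 90% line (11/12 to 11/13). These figures assume that the left-out patient is a failure and that the full 12 or 17 are reached. The true number of such withdrawals is unknown, at most about 6 of 18. Upward bias is plausible given the reasons in 3.4.1, but it is not demonstrated.

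For untreatable patients, the only finding is that the patients-treated labels in 7.1.3 and 7.1.4 must be reconciled with the note and with criterion (a), under which such a patient is an infeasibility event.

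**What to change.** 1. Define one feasibility set: eligible, consented patients who begin proton planning, whether or not they are then treated.
2. Use that set in the 7.1.3 table and the 7.1.4 analyses in place of patients treated.
3. Count withdrawal before completion of radiotherapy as infeasible, unless the documented reason is unrelated to treatment.
4. Report the evaluable-only rate as a sensitivity analysis, with the number of patients left out and their reasons.
5. For patients already enrolled, keep the infeasibility definition that was current at their enrolment, as 7.1.4 requires. Show any excluded withdrawals in a sensitivity analysis and do not re-grade them.

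The cost is a change of text and a look back at earlier withdrawals. No new data are needed, because 3.4.1 already requires reasons to be documented. The feasibility rate may come out slightly lower. Counting withdrawals with a doubtful reason as failures may make it somewhat conservative, which is why both rates should be reported.

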### 7.1.2 Endpoints

### 7.1.2.1 Primary Endpoints

Feasibility will be based on multiple radiation planning and treatment parameters. For proton to be deemed feasible, no greater than 10% of patients should experience one of the following events: a) Patient cannot be given treatment because anatomy is such that a dosimetrically satisfactory treatment plan cannot be devised. For example, the dosimetry is unsatisfactory if

<95% of target volume is covered by 95% of the dose, b) Patient receives greater than 50% of their total treatment (for any reason-unable to set patient up within acceptable limits of tolerance, patient unable to tolerate treatment position or immobilization for duration of treatment) with photon beam radiotherapy (using a backup photon plan, c) Patient is unable to complete all of his/her treatments within 10 days of estimated date of treatment completion or requires a treatment break greater than 5 days.

Acute Toxicity is defined as any grade 3 or higher toxicity, considered probably or definitely related to radiation, observed within 90 days from start of therapy, excluding cranial nerve palsies or nerve root symptoms as these may be due to the tumor itself or prior surgery. Toxicities will be graded using the NCI Common Terminology Criteria for Adverse Events (CTCAE) Version 4.0.

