# 2 Study Objectives

This study will be done in two phases. In the first phase, feasibility will be established using the primary objectives set below. The second phase will begin no earlier than 90 days after the last patient in the initial phase has started treatment and once safety and feasibility has been verified. The secondary objectives will serve as the objectives for the second phase of the study.

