#### **Primary Objective**

The primary objective of this study is feasibility. The study will be deemed infeasible if greater than 10% of pts experience one of the following:

- a. Patient cannot be given treatment because anatomy is such that a dosimetrically satisfactory treatment plan cannot be devised as defined in Section 4.5.1.
- b. For base of skull patients only. Patient receives greater than 40% of their total treatment (for any reason, i.e. unable to set patient up within acceptable limits of tolerance, patient unable to tolerate treatment position or immobilization for duration of treatment) with photon beam radiotherapy (using a backup photon plan).

For spine and all other patients. Patient receives greater than 20% of their total treatment (for any reason, i.e. unable to set patient up within acceptable limits of tolerance, patient unable to tolerate treatment position or immobilization for duration of treatment) with photon beam radiotherapy (using a backup photon plan).

- c. Patient is unable to complete all of his/her treatments within 10 days of estimated date of treatment completion or requires a treatment break greater than 5 days.
- d. Additionally, no greater than 20% of patients experience an unexpected acute toxicity > Grade 3 that is probably or definitely related to radiation therapy.

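### The photon-share limit in the primary feasibility endpoint is stated two ways (over 40% or 20% by site in Section 2; over 50% for everyone in Section 7.1.2.1), and the plan does not say which is the new definition

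*Combined protocol and SAP*

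**What the plan says.** The same event, one of three that make a patient infeasible, is defined in two places.

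- Section 2, Primary Objective, item b, splits by site. One limit reads "For base of skull patients only. Patient receives greater than 40% of their total treatment". The other reads "For spine and all other patients. Patient receives greater than 20% of their total treatment".
- Section 7.1.2.1, Primary Endpoints, item b, has a single limit with no mention of site: "Patient receives greater than 50% of their total treatment".

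Both sections then apply the same criterion: proton therapy is not feasible if more than 10% of patients have one of the listed events.

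Two places point towards Section 2. Its opening says that "feasibility will be established using the primary objectives set below". A note on evaluability in Section 7.1.1 speaks of patients "unable to undergo proton treatment as defined in section 2.0 or have a significant acute toxicity as these are feasibility criteria".

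Sections 7.1.4 and 7.3 say that 12 additional base of skull patients will be judged by a new definition of feasibility. Neither section gives that definition or says where to find it. Section 7.1.4 adds that each patient is judged by the definition that was "current when the patient enrolled on the trial", with no later re-grading of base of skull patients. The posterior probability that the feasibility rate exceeds 90% is to be calculated two ways, "based on all 26 patients treated and on all 17 patients treated after the modification".

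**The concern.** Two sets of limits for one component of the primary endpoint mean that the number of infeasible patients depends on which page the analyst opens. Section 7.1.2.1 carries the heading for primary endpoints, so it is the natural place to look, and it has the more lenient limit. Patients with a photon share above 40% (base of skull) or 20% (spine and other) but not above 50% are infeasible under Section 2 and feasible under Section 7.1.2.1.

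Such patients are possible. Section 4.4.1 adds IMRT dose to proton dose, and Section 4.5.2 allows IMRT backup plans and partial treatments.

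The count feeds the posterior probability in 7.1.4, the termination table in 7.1.3 and the decision to open Phase II. The rule that ties each patient to the definition in force at enrolment makes a clear label more necessary, because it presumes that every patient has one identifiable definition.

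**Working it through.** **Inputs.** Limits of 40% and 20% (Section 2, item b) and 50% (Section 7.1.2.1, item b); 10% criterion (both sections); Beta(5,1) prior (Section 7.1.3); total dose 70.2 to 79.2 Gy in 39 to 44 fractions of 1.8 Gy, with 1 Gy of photons counted as 1 Gy (RBE) (Section 4.4.1); analysis sets of 26 and 17 patients (Section 7.1.4), which leave 26 − 17 = 9 enrolled before the modification.

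**1. The plan's own figures.** With *f* feasible of *n*, the posterior is Beta(5 + *f*, 1 + *n* − *f*), and the quantity of interest is its probability above 0.90.

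| Feasible / treated | Recomputed | Printed in 7.1.3 |
|---|---|---|
| 1/3 | 0.038 | 0.04 |
| 4/6 | 0.090 | 0.09 |
| 6/9 | 0.044 | 0.04 |
| 9/12 | 0.083 | 0.08 |

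The termination table is sound. The defect is in the event definition that feeds it.

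**2. Width of the gap.** Both definitions refer to total treatment without saying how the share is measured. If it is measured by dose *D*, the two texts disagree for photon dose in (0.4*D*, 0.5*D*] for base of skull and (0.2*D*, 0.5*D*] for spine and other.

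| Total dose (Gy) | Base of skull (Gy) | Spine and other (Gy) |
|---|---|---|
| 70.2 | 28.08 to 35.10 | 14.04 to 35.10 |
| 72.0 | 28.80 to 36.00 | 14.40 to 36.00 |
| 73.8 | 29.52 to 36.90 | 14.76 to 36.90 |
| 79.2 | 31.68 to 39.60 | 15.84 to 39.60 |

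If it is measured in equal fractions, the gap at 40 fractions runs from 16 + 1 = 17 to 20 photon fractions (base of skull) and from 8 + 1 = 9 to 20 (spine and other). At 44 fractions it is 18 to 22 and 9 to 22.

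**3. Effect of one patient in the gap.** With *k* infeasible of *n*, the posterior is Beta(5 + *n* − *k*, 1 + *k*). The patient is assumed not to be infeasible for another reason.

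| *n* | *k* | Observed infeasible | P(rate > 90%) |
|---|---|---|---|
| 12 | 1 → 2 | 8.3% → 16.7% | 0.52 → 0.24 |
| 12 | 2 → 3 | 16.7% → 25.0% | 0.24 → 0.08 |
| 17 | 1 → 2 | 5.9% → 11.8% | 0.66 → 0.38 |
| 26 | 2 → 3 | 7.7% → 11.5% | 0.61 → 0.38 |

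The first, third and fourth rows cross the 10% criterion. The second reaches the printed termination boundary of 9 feasible of 12, at which termination is to be considered. That table stops at 12 patients and is not extended here.

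**4. How often.** The documents give no frequency. Purely as an assumption, if 1%, 5% or 10% of patients fall in the gap independently, the chance of at least one among 17 is 1 − (1 − *p*)^17 = 16%, 58% or 83%. Among the 12 base of skull patients alone it is 11%, 46% or 72%.

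**The case against.** The best reply is that the documents already lean one way. The opening of Section 2 and the note in 7.1.1 both point to Section 2. Only Section 2 carries the split by site that the revised sample size uses. Nothing points to the 50% limit, which looks like text left over at the amendment. Earlier patients are covered by the enrolment-date rule, and the approved versions must exist because Section 11.0 sends amendments to the IRB.

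This is a fair reading and probably the right one, but it is an inference. No text marks the 50% limit as superseded or confines it to an enrolment period. The note in 7.1.1 concerns who is evaluable, not which definition prevails. A primary endpoint should not have to be inferred.

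Some objections to the size do stand:

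- Section 7.1.4 sets no success threshold for the posterior, so the shifts in it cross no stated posterior rule except the boundary at 9 of 12. The decision that can flip is the 10% criterion.
- Not every reclassified patient matters. Going from 0 to 1 infeasible of 12 stays under 10%.
- The assumed frequencies are illustrative. The figure of 17 is a maximum, since there is no target number of spine patients, and one rate is applied to two gaps of different width.
- The dose gap assumes that the share is counted by dose. Section 4.5.2 suggests that photons follow the same scheme, in which case dose and fraction counts agree.

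Two related mismatches are lesser. The target-coverage figure in 7.1.2.1, item a, is only an example, and Section 2 defers to 4.5.1. Whether related acute toxicity counts towards feasibility (Sections 2 item d, 4.6 and 7.1.2.1) is a separate question.

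**Conclusion.** The concern holds: the plan is wrong as written and needs correction before the feasibility analysis. Current text gives conflicting numerical limits for one event in the primary endpoint: 50% against 40% for base of skull, and 50% against 20%, a 2.5-fold difference, for spine and other patients. The new definition on which the analysis depends is not identified.

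A single patient between the limits can reverse the 10% criterion at each of the three sample sizes examined (12, 17 and 26). This rests on the Beta(5,1) prior, on that patient having no other infeasibility event, and on the count otherwise lying just under the limit. Whether any patient falls in the gap cannot be known from the documents.

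The firm part of the conclusion concerns patients enrolled after the amendment. For the 9 earlier patients a rule exists, but the version it refers to is not named.

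**What to change.** Reconcile Section 2, item b, and Section 7.1.2.1, item b, against the approved version history, so that both print the same definition for patients enrolled after the amendment. In Section 7.1.4, name the protocol version and enrolment period that govern the up to 17 post-amendment patients and the 9 earlier ones, and state that this is the new definition meant in 7.1.4 and 7.3. Say also whether the photon share is measured by dose or by fractions. The limits should come from the version history and not be chosen once results are known; none is recommended here.

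In the same amendment, align the coverage example in 7.1.2.1 with 4.5.1, and reconcile Sections 2 item d, 4.6 and 7.1.2.1 on whether related acute toxicity counts towards feasibility.

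The cost is a wording amendment and a check of past versions. The only data needed are delivered photon and proton treatment and enrolment dates. If the history confirms the stricter limits, the reported feasibility rate can be lower than under 50%, and with few patients even one reclassification could change the conclusion.
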